3.2. Primary Outcomes

- 1) Prevalence of a positive response to NAC, defined at each dose as any sneezing score of 3 or a TNSS ≥ 8 out of 12 in Phase 1 or a TNSS ≥ 6 out of 12 in Phase 2.
- 2) Safety - number of reported adverse events and serious adverse events, including their severity, seriousness, and relatedness to study procedures.

3.3. Secondary Outcomes

- 1) Number of Sneezes – summarized across all participants at each dose
- 2) TNSS – highest score out of all doses received
- 3) TNSS – change from baseline
- 4) Change in PNIF from baseline
- 5) Change in PEF from baseline
- 6) Visual Analog Scale (VAS) - change from baseline
- 7) Change in tryptase in nasal secretions
- 8) Change in albumin in nasal secretions

3.4. Exploratory Outcomes

- 1) Change in chemokines and other biomarkers in nasal secretions
- 2) Change in cockroach-specific T-cell epitopes in peripheral blood

3.5. Symptom scoring

The systems for symptom scoring for use in tabulating clinical responses before or after allergen exposure are described in Table 3.5 and Figure 3.5.

[figure not shown]
[figure not shown]
[figure not shown]
[figure not shown]
[figure not shown]
[figure not shown]
Symptom scores will be assessed at the following time points or as described in the MOP for Protocol ICAC-27:

- Baseline – pre and post nasal rinse
- After each NAC dose administration

Table 3.5. Total Nasal Symptom Score (TNSS)

Category	Measurement	Points
Sneezing Sneeze Count = —	none	0
	1-2	1
	3-4	2
	5 or more	3
Runny nose	None - my nose feels fine and not runny at all	0
	Mild - my nose is a little runny; I might be able to blow a little snot or mucous out	1
	Moderate - my nose is very runny; I could definitely blow out some snot or mucous	2
	Severe - my nose is extremely runny; I could blow out a lot of snot or mucous	3
Stuffy nose	None - my nose feels fine; I am not at all stuffy or congested	0
	Mild - my nose feels a little stuffy	1
	Moderate - my nose feels very stuffy; it is hard to breathe through my nose	2
	Severe - my nose is completely stuffy; I cannot even breathe through my nose	3
Itchy Nose	None - my nose does not itch at all	0
	Mild - my nose feels a little itchy	1
	Moderate - my nose feels very itchy	2
	Severe - my nose is extremely itchy	3
TNSS		/12

Figure 3.5. Visual Analog Scale (VAS)

Nasal Symptoms:		
Sneezing		As Bad as I Can Imagine
No Symptoms		As Bad as I Can Imagine
Runny nose		As Bad as I Can Imagine
No Symptoms		As Bad as I Can Imagine
Stuffy nose		As Bad as I Can Imagine
No Symptoms		As Bad as I Can Imagine
Itchy nose		As Bad as I Can Imagine
No Symptoms		As Bad as I Can Imagine
Overall:		
No Symptoms		As Bad as I Can Imagine

Please mark with a single vertical (up and down) line for how you feel **RIGHT NOW for each symptom, as shown to you by the staff.**

4. Selection of Participants and Clinical Sites/Laboratories

4.1. Rationale for Study Population

Because the combination of cockroach allergy and cockroach exposure is one of the most important factors contributing to the dramatically increased asthma morbidity seen in inner city children with asthma, a major ICAC goal is to conduct a large multi-center efficacy trial of cockroach immunotherapy in this population. Direct instillation of allergen to the nose via a NAC has been studied as a surrogate measure of allergic reactivity. Another DAIT NIAID-sponsored clinical trial (Protocol ITN 057AD, IND #117,529) conducted in conjunction with the Immune Tolerance Network, incorporated a NAC followed by measurement of nasal responses as a way of quantifying treatment efficacy for individuals with cat allergy. However, cockroach allergen has not been previously used in a NAC, and the tolerability and appropriate dose range for administration to children with asthma is unknown. The first phase of this study will recruit adults in order to establish a range of doses of cockroach allergen that can be safely administered to cockroach sensitive children with asthma.

4.2. Inclusion Criteria

Individuals who meet all of the following criteria are eligible for enrollment as study participants for Phase 1a and Phase 2:

1. Subject and/or parent guardian must be able to understand and provide informed consent

2. Male or female adults, 18 through 55 years of age at recruitment (Phase 1) or male or female children, 8-14 years of age at recruitment (Phase 2)
3. Have a history of asthma for a minimum of 1 year before study entry:
 - a. A diagnosis of asthma will be defined as a report by the participant that they have had a clinical diagnosis of asthma made by a physician over a year ago.
 - b. The participant must have persistent asthma defined by the current need for at least 100 mcg fluticasone per day or the equivalent of another inhaled corticosteroid.
 - c. The participant's asthma must be well controlled as defined by:
 - i. A FEV1 greater than or equal to 80% predicted (see Section 8.2).
 - ii. An Asthma Control Test (ACT) score ≥ 20 .
4. Are sensitive to German Cockroach as documented by a positive (≥ 3 mm greater than negative control) skin prick test result and a positive German Cockroach specific IgE (≥ 0.35 kUA/L).
5. Have no known contraindications to the allergenic extracts or diluents.

Individuals who meet the following criteria are eligible for enrollment as study participants in Phase 1b after completion of Phase 1a:

1. The participant's asthma must be well controlled as defined by:
 - a. A FEV1 greater than or equal to 80% predicted (see Section 8.2).
 - b. An Asthma Control Test (ACT) score ≥ 20 .
2. The participant tolerated the NAC during Phase 1a with no AEs grade 2 or higher as determined by Table 12.3.1a Grading of Local Reactions to Study Procedures.

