11. Past or current medical problems or findings from physical examination or laboratory testing that are not listed above, which, in the opinion of the investigator, may pose additional risks from participation in the study, may interfere with the participant's ability to comply with study requirements or that may impact the quality or interpretation of the data obtained from the study.

Individuals are not eligible for enrollment as study participants in Phase 1b after completion of Phase 1a if any of the following criteria are met:

1. Are pregnant or lactating.
2. Have an asthma severity classification of severe persistent, using the NAEPP classification, as evidenced by at least one of the following:
 - a. Require a dose of greater than 500 mcg of fluticasone per day or the equivalent of another inhaled corticosteroid.
 - b. Have received more than 2 courses of oral or parenteral corticosteroids within the last 12 months or one course within the last 3 months.
 - c. Have been treated with depot corticosteroids within the last 12 months.
 - d. Have been hospitalized for asthma within the 12 months prior to their participation in Phase 1b.
 - e. Have had an emergency room visit for asthma within the 3 months prior to their participation in Phase 1b.
 - f. Have had a life-threatening asthma exacerbation that required intubation, mechanical ventilation, or that resulted in a hypoxic seizure within 2 years prior to their participation in Phase 1b.
3. Have received allergen immunotherapy (SLIT or SCIT) in the last 12 months prior to their participation in Phase 1b.
4. Have previously been treated with anti-IgE therapy in the 12 months prior to their participation in Phase 1b.
5. Are currently receiving oral or nasal antihistamines, nasal corticosteroids, nasal decongestants, nasal anticholinergics or cromolyn, which cannot be suspended for the required washout periods prior to the nasal allergen challenge in Phase 1b.
6. Have received an investigational drug in the 30 days prior to their participation in Phase 1b.
7. Have past or current medical problems or findings from physical examination or laboratory testing that are not listed above, which, in the opinion of the investigator, may pose additional risks from participation in the study, may interfere with the participant's ability to comply with study requirements or that may impact the quality or interpretation of the data obtained from the study.

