8. Meet any of the Participant Stopping Rules and Withdrawal Criteria during Phase 1a

- a. The participant elected to withdraw consent from all future study activities, including follow-up.
- b. The participant died.
- c. The Investigator no longer believes participation is in the best interest of the participant.
- d. SAE related to investigational product
- e. Anaphylactic reaction grade 2 or 3 (see Table 12.3.1c)
- f. Inability to tolerate the NAC prior to reaching a TNSS ≥ 8 or a sneezing score of 3 due to excessive discomfort or symptoms
- g. Epistaxis occurring during the Challenge Visit
- h. The need to start immunotherapy or any chronic immunosuppressive medications in the period between Phase 1a and Phase 1b
- i. Require a dose of greater than 500 mcg of fluticasone per day or the equivalent of another inhaled corticosteroid to maintain asthma control in the period between Phase 1a and Phase 1b
- j. Inability to restrict use of antihistamines, nasal steroids, nasal decongestants, nasal anticholinergics or cromolyn prior to the NAC according to the period specified in the ICAC medication washout guidelines described in the MOP for Protocol ICAC-27
- k. Development of any serious medical illness whose natural history, sequela, or treatment would be worsened or impaired by continuation in the protocol
- l. Participant is “lost to follow-up,” as defined in the MOP for Protocol ICAC-27.

9. The participant’s initial TNSS at the Repeat Challenge Visit must be within 1 point of the initial TNSS at the Challenge Visit in Phase 1a. If the participant’s initial TNSS is outside the 1 point range, then the participant may be reevaluated for the Repeat Challenge Visit up to 3 additional times.

Participants who meet any of the following criteria are not eligible for enrollment in any portion of the study and may not be reassessed. Participants are ineligible if they:

1. Plan to move from the area during the study period.
2. Have a history of idiopathic anaphylaxis or anaphylaxis grade 2 or higher as defined in Table 12.3.1c
3. Have unstable angina, significant arrhythmia, uncontrolled hypertension, history of autoimmune disease, or other chronic or immunological diseases that in the opinion of the investigator might interfere with the evaluation of the investigational agent or pose additional risk to the participant.
4. Are using tricyclic antidepressants or beta-adrenergic blocker drugs (both oral and topical).

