6.4. Premature Discontinuation of Investigational Product

Participants, who are prematurely discontinued for safety reasons after receiving at least one dose of investigational product during the Challenge Visit, will not be replaced. Participants who are prematurely discontinued, but who did not receive a dose of investigational product may be replaced.

Study procedures may be prematurely discontinued for any participant for any of the following reasons:

1. SAE related to investigational product
2. Anaphylactic reaction grade 2 or 3 (see Table 12.3.1c)
3. Inability to tolerate the dose escalation during the NAC due to excessive discomfort/symptoms
4. Reduction in FEV₁ of more than 15% from baseline and/or reduction of PEF by more than 20% from baseline and inability to perform spirometry due to administration of rescue medications during the course of the nasal allergen challenge.
5. Development of any serious medical illness whose natural history, sequela, or treatment would be worsened or impaired by continuation in the protocol

7. Other Medications

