11.2. Participant Stopping Rules and Withdrawal Criteria

Participants may be prematurely terminated from the study for the following reasons:

1. The participant elects to withdraw consent from all future study activities, including follow-up.
2. The participant dies.
3. The Investigator no longer believes participation is in the best interest of the participant.
4. SAE related to investigational product
5. Anaphylactic reaction grade 2 or 3 (see Table 12.3.1c)
6. Inability to tolerate the NAC prior to reaching a sneezing score of 3 or a TNSS ≥ 8 (Phase 1) or a TNSS ≥ 6 (Phase 2) due to excessive discomfort or symptoms
7. Epistaxis occurring during the Challenge visit
8. The need to start immunotherapy or any chronic immunosuppressive medications in the period between the Screening and Challenge Visits
9. Require a dose of greater than 500 mcg of fluticasone per day or the equivalent of another inhaled corticosteroid to maintain asthma control in the period between the Screening and Challenge Visits

10. Inability to restrict use of antihistamines, nasal steroids, nasal decongestants, nasal anticholinergics or cromolyn prior to the NAC according to the period specified in the ICAC medication washout guidelines described in the MOP for Protocol ICAC-27
11. Development of any serious medical illness whose natural history, sequela, or treatment would be worsened or impaired by continuation in the protocol
12. Participant is "lost to follow-up," as defined in the MOP for Protocol ICAC-27.

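### Phase 1b assesses Phase 1a tolerance by local reactions only, so an isolated lower-airway reaction at the threshold dose meets no event-specific bar to rechallenge

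*Protocol*

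**What the plan says.** Phase 1b inclusion 2 (Protocol 4.2, with matching text in 8.4 and the synopsis) admits adults who tolerated the first challenge with "no AEs grade 2 or higher as determined by Table 12.3.1a Grading of Local Reactions to Study Procedures". Section 12.3.1 reserves that table for excessive local reactions without systemic features. PEF declines at the Challenge Visit go to Table 12.3.1b, except that a decline is not an AE if spirometry then shows FEV1 at 85% of baseline or better.

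Phase 1b exclusion 8 (4.3) bars adults who "Meet any of the Participant Stopping Rules and Withdrawal Criteria during Phase 1a" and lists those events as a to l, drawn from 11.2. They include "Inability to tolerate the NAC prior to reaching a TNSS" of 8 or a sneezing score of 3 because of discomfort or symptoms (8f), and "Epistaxis occurring during the Challenge Visit" (8g).

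Section 6.4 gives its own reasons for discontinuation. Item 3 is "Inability to tolerate the dose escalation during the NAC due to excessive discomfort/symptoms". Item 4 is a separate reason: a reduction in FEV1 "of more than 15% from baseline and/or reduction of PEF by more than 20% from baseline", the PEF limb applying when rescue medication prevents spirometry. Item 4 is in neither 11.2 nor exclusion 8. Study stopping rule 4b (11.5) uses the same lung-function event, if considered related, once at least 2 participants have it.

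**The concern.** Section 5.1.1 names provoked asthma as a risk of the challenge, and every participant has persistent asthma. One would expect the rules for repeat exposure to ask first whether the earlier exposure caused a lower-airway reaction. The event-specific criteria ask about nosebleeds, anaphylaxis, related SAEs, intolerance before threshold and oral steroids for a local reaction, but not about a confirmed fall in lung function.

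The result is uneven. Epistaxis at the first challenge is a listed bar. An FEV1 loss that counts toward suspending the whole study is not, and the documents give no reason for the difference. At stake is the safety of up to 10 adults who may receive up to 8 further allergen doses from day 30 onward. Consistency is also at stake: the SAP (7.1.1) names five study sites, and their investigators could decide the same case differently.

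**Working it through.** **1. The example.** An adult reaches TNSS 8. At the same assessment PEF is 65% and FEV1 80% of baseline. There are no other systemic features, and the adult recovers on site. The timing is plausible, because 8.3 places TNSS and PEF in the same 10 to 20 minute window after each dose.

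- PEF of 65% lies in the 69–50% band, so it is grade 3 in Table 12.3.1b.
- FEV1 of 80% is below 85%, so the exemption does not apply and the event remains an AE.
- The FEV1 fall is 100% − 80% = 20%, which exceeds 15%. It meets 6.4 item 4 and, if considered related, counts toward rule 4b.

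**2. The example against the Phase 1b criteria that bear on it.**

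| Criterion | Result |
|---|---|
| Inclusion 1 (FEV1 at least 80% predicted, ACT at least 20) | Met after recovery; describes the day of rechallenge, not the Phase 1a reaction |
| Inclusion 2 (Table 12.3.1a) | Met; no local reaction of grade 2 or higher |
| Exclusion 2b, 2d, 2e (steroid course, hospitalization, emergency visit) | Not triggered; none occurred |
| 8d (related SAE) | Not triggered; the event is not an SAE |
| 8e (anaphylaxis grade 2 or 3) | Not triggered; the Table 12.3.1c footnote leaves out respiratory symptoms that occur alone during the challenge |
| 8f (intolerance before threshold) | Not triggered; the threshold was reached |
| 8g (epistaxis) | Not triggered |
| 6.4 item 4 | Not among the Phase 1b criteria |
| Exclusions 7 and 8c | Investigator opinion only |

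8f cannot be stretched to cover the case. It is limited to the period before threshold and to discomfort or symptoms, and 6.4 treats intolerance (item 3) and lung-function falls (item 4) as different reasons.

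**3. Time limits.** Exclusion 2e reads "Have had an emergency room visit for asthma within the 3 months prior to their participation in Phase 1b", and the single-steroid-course limit in 2b is also 3 months. The rechallenge window is 30 to 365 days (3.1), so either limit can lapse inside it.

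**4. Size.** There are at most 10 adults. The documents give no rate for FEV1 falls of more than 15%, so one must be assumed. Section 5.1.1 cites one slight (10%) FEV1 drop among 50 children given other allergens. Assume that none of the 50 exceeded 15%:

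- Exact 95% interval for 0/50: 0 to 1 − 0.025^(1/50) = 0.0711.
- Expected number among 10 adults: 0 to 10 × 0.0711 = 0.71.
- Chance of at least one, 1 − (1 − p)^10: 0 at p = 0; 0.096 at p = 0.01; 0.183 at p = 0.02; 0.522 at p = 0.0711.
- At p = 0.02, the chance of exactly one is 10 × 0.02 × 0.98^9 = 0.167. Most of the 0.183 is therefore a single case, which does not reach the 2-participant count in rule 4b.

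These are upper figures for the gap, because they include falls that other criteria or the investigator would exclude.

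**The case against.** The strongest reply is that the protocol already allows such an adult to be kept out. Exclusion 7 covers medical problems that the investigator thinks add risk, and 8c covers the participant's best interest. Section 6.4 lets study procedures be discontinued for this very FEV1 fall, and the repeat challenge is a study procedure. Section 11.2 is also only permissive: "Participants may be prematurely terminated from the study for the following reasons". All of that stands as discretion. The difference is that exclusion 8 turns the 11.2 events into bars for Phase 1b, and nothing does the same for 6.4 item 4.

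It can also be said that the nasal-challenge row of Table 12.3.1a grades by treatment needed and names no organ, so treated bronchospasm might be placed there. The row does leave some room. But the table's title and 12.3.1 confine it to local reactions, and 12.2.1 sends PEF to Table 12.3.1b separately.

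The repeat challenge is itself guarded. Asthma must be controlled, dosing restarts at diluent and escalates, PEF is read after each dose, the challenge stops if FEV1 is below 85% of baseline, and a physician is immediately available. This lowers the risk from a wrong admission, but it does not decide who should be admitted.

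A reader might infer that any adult with a recorded lower-airway reaction passes every rechallenge criterion. The documents do not support that. A related SAE, anaphylaxis of grade 2 or 3, symptoms that end the challenge before threshold, hospitalization for asthma within 12 months, and a steroid course or emergency visit within 3 months all exclude. Nor do the documents report that such a reaction occurred in Phase 1a.

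**Conclusion.** The point holds in a limited form. The event-specific Phase 1b criteria do not bar an adult whose isolated lower-airway reaction coincides with reaching the nasal threshold, is neither an SAE nor anaphylaxis, and leads to no recent steroid course, emergency visit or hospitalization. Only discretion under exclusions 7 and 8c and the permissive wording of 6.4 applies.

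This rests on the text and not on a rate. The 0% to 52% chance of at least one FEV1 fall above 15% among 10 adults depends on an assumed 0/50 from children given other allergens, and it overstates the gap. Protocol 3.1 already reports Phase 1a findings, so the actual number can be counted and may be zero. It is a worthwhile, inexpensive safety amendment and does not bear on the primary analysis.

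**What to change.** - In Phase 1b inclusion 2 (4.2, 8.4 and the synopsis, which the SAP repeats), require no AE of grade 2 or higher under Table 12.3.1a or Table 12.3.1b.
- Add 6.4 item 4 to 11.2 and to Phase 1b exclusion 8 (4.3, 8.4 and the synopsis). This also covers an FEV1 loss above 15% when the PEF fall is only grade 1.
- Leave eligible those adults whose PEF fell but whose FEV1 was at least 85% of baseline, since 12.3.1 does not count that as an AE.
- If a bronchospasm clause is wanted, for instance for late reactions outside Table 12.3.1b, limit it to investigator-confirmed bronchospasm related to the challenge and recorded as an AE of grade 2 or higher. Barring any bronchodilator use would be too broad: these adults have persistent asthma and are told to carry albuterol for 24 hours.
- Check the Phase 1a records (at most 10) against the new wording before any further repeat challenge.

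The cost is a few lines of text and a short record check. The downside is that each adult excluded is lost from a reproducibility sample of at most 10. If the sponsor prefers to keep such adults eligible, the protocol should say why.

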4.3. Exclusion Criteria

Individuals who meet any of these criteria are not eligible for enrollment as study participants in Phase 1a and Phase 2:

1. Are pregnant or lactating. Post-menarcheal females must be abstinent or use a medically acceptable birth control method throughout the study (e.g. oral, subcutaneous, mechanical, or surgical contraception).
2. Cannot perform spirometry at Screening.
3. Have an asthma severity classification at Recruitment of severe persistent, using the NAEPP classification, as evidenced by at least one of the following:
 - a. Require a dose of greater than 500 mcg of fluticasone per day or the equivalent of another inhaled corticosteroid.
 - b. Have received more than 2 courses of oral or parenteral corticosteroids within the last 12 months or one course within the last 3 months.
 - c. Have been treated with depot corticosteroids within the last 12 months.
 - d. Have been hospitalized for asthma within the 12 months prior to recruitment.
 - e. Have had an emergency room visit for asthma within the 3 months prior to recruitment.
 - f. Have had a life-threatening asthma exacerbation that required intubation, mechanical ventilation, or that resulted in a hypoxic seizure within 2 years prior to recruitment.
4. Have nasal polyps or other major structural abnormalities in their nasal cavities as assessed by anterior rhinoscopy.
5. Have active rhinitis symptoms prior to the nasal allergen challenge, defined as a Baseline TNSS >3 , with no individual symptom score >1 .

6. Do not have access to a phone (needed for scheduling appointments).
7. Have received allergen immunotherapy (SLIT or SCIT) in the last 12 months prior to recruitment or who plan to initiate or resume allergen immunotherapy during the study.
8. Have previously been treated with anti-IgE therapy in the 12 months prior to recruitment.
9. Are currently receiving oral or nasal antihistamines, nasal corticosteroids, nasal decongestants, nasal anticholinergics or cromolyn, which cannot be suspended for the required washout periods prior to skin prick testing and the nasal allergen challenge.
10. Have received an investigational drug in the 30 days prior to recruitment or who plan to use an investigational drug during the study.
11. Past or current medical problems or findings from physical examination or laboratory testing that are not listed above, which, in the opinion of the investigator, may pose additional risks from participation in the study, may interfere with the participant's ability to comply with study requirements or that may impact the quality or interpretation of the data obtained from the study.

Individuals are not eligible for enrollment as study participants in Phase 1b after completion of Phase 1a if any of the following criteria are met:

1. Are pregnant or lactating.
2. Have an asthma severity classification of severe persistent, using the NAEPP classification, as evidenced by at least one of the following:
 - a. Require a dose of greater than 500 mcg of fluticasone per day or the equivalent of another inhaled corticosteroid.
 - b. Have received more than 2 courses of oral or parenteral corticosteroids within the last 12 months or one course within the last 3 months.
 - c. Have been treated with depot corticosteroids within the last 12 months.
 - d. Have been hospitalized for asthma within the 12 months prior to their participation in Phase 1b.
 - e. Have had an emergency room visit for asthma within the 3 months prior to their participation in Phase 1b.
 - f. Have had a life-threatening asthma exacerbation that required intubation, mechanical ventilation, or that resulted in a hypoxic seizure within 2 years prior to their participation in Phase 1b.
3. Have received allergen immunotherapy (SLIT or SCIT) in the last 12 months prior to their participation in Phase 1b.
4. Have previously been treated with anti-IgE therapy in the 12 months prior to their participation in Phase 1b.
5. Are currently receiving oral or nasal antihistamines, nasal corticosteroids, nasal decongestants, nasal anticholinergics or cromolyn, which cannot be suspended for the required washout periods prior to the nasal allergen challenge in Phase 1b.
6. Have received an investigational drug in the 30 days prior to their participation in Phase 1b.
7. Have past or current medical problems or findings from physical examination or laboratory testing that are not listed above, which, in the opinion of the investigator, may pose additional risks from participation in the study, may interfere with the participant's ability to comply with study requirements or that may impact the quality or interpretation of the data obtained from the study.

8. Meet any of the Participant Stopping Rules and Withdrawal Criteria during Phase 1a

- a. The participant elected to withdraw consent from all future study activities, including follow-up.
- b. The participant died.
- c. The Investigator no longer believes participation is in the best interest of the participant.
- d. SAE related to investigational product
- e. Anaphylactic reaction grade 2 or 3 (see Table 12.3.1c)
- f. Inability to tolerate the NAC prior to reaching a TNSS ≥ 8 or a sneezing score of 3 due to excessive discomfort or symptoms
- g. Epistaxis occurring during the Challenge Visit
- h. The need to start immunotherapy or any chronic immunosuppressive medications in the period between Phase 1a and Phase 1b
- i. Require a dose of greater than 500 mcg of fluticasone per day or the equivalent of another inhaled corticosteroid to maintain asthma control in the period between Phase 1a and Phase 1b
- j. Inability to restrict use of antihistamines, nasal steroids, nasal decongestants, nasal anticholinergics or cromolyn prior to the NAC according to the period specified in the ICAC medication washout guidelines described in the MOP for Protocol ICAC-27
- k. Development of any serious medical illness whose natural history, sequela, or treatment would be worsened or impaired by continuation in the protocol
- l. Participant is “lost to follow-up,” as defined in the MOP for Protocol ICAC-27.

9. The participant’s initial TNSS at the Repeat Challenge Visit must be within 1 point of the initial TNSS at the Challenge Visit in Phase 1a. If the participant’s initial TNSS is outside the 1 point range, then the participant may be reevaluated for the Repeat Challenge Visit up to 3 additional times.

Participants who meet any of the following criteria are not eligible for enrollment in any portion of the study and may not be reassessed. Participants are ineligible if they:

1. Plan to move from the area during the study period.
2. Have a history of idiopathic anaphylaxis or anaphylaxis grade 2 or higher as defined in Table 12.3.1c
3. Have unstable angina, significant arrhythmia, uncontrolled hypertension, history of autoimmune disease, or other chronic or immunological diseases that in the opinion of the investigator might interfere with the evaluation of the investigational agent or pose additional risk to the participant.
4. Are using tricyclic antidepressants or beta-adrenergic blocker drugs (both oral and topical).

5. Known and Potential Risks and Benefits to Participants

